4.1. Eligibility and exclusion criteria for CESTA participation (Modules 1 and 2)

4.1.1. Eligibility criteria

1. Willing to disclose HIV status

- 2. HIV negative women aged 30-54 years; HIV positive women aged 25-54 years
- 3. Mentally competent to give informed consent
- 4. Physically able to have a pelvic exam

4.1.2. Exclusion criteria

- 1. Women reporting no previous sexual activity
- 2. History of cervical cancer
- 3. Treatment for cervical precancer in the last six months
- 4. Hysterectomy
- 5. Pregnancy
- 6. Serious pre-existing medical conditions (e.g. history of bleeding disorders, serious physical or mental disease)

4.2. Randomisation procedures

The method of randomization will be through the use of pre-printed cards. Each randomisation will have its own set of cards with allocations to one of the screen-and-treat study arms (1: HPV + VIA + treatment or 2: HPV + treatment) and to one of the treatment arms (A: cryotherapy or B: thermal ablation). The Soares big stick design (BSD) [29] algorithm will be used. This algorithm assures the best allocation randomness in a comparison of 14 methods [30]. Using R software, the output of this algorithm is a csv file with the participant number and the arm allocation. The same procedure will be applied on HIV positive and HIV negative women included in the study.

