- 9. To explore the acceptability of thermal ablation versus cryotherapy among treated women.

3.2. Study outline CESTA Module 1

The CESTA Module 1 is a double-level randomized study with the main objective to evaluate the efficacy of two cervical screen-and-treat algorithms in HIV positive and HIV negative women separately.

3.2.1. CESTA Module 1 among HIV positive women in South Africa (see figure 2)

3000 HIV-positive women will be screened with HPV testing and HPV-positive women will be randomized in a 4:1 ratio to be triaged by VIA and treated (arm 1, HPV+VIA+treat) or treated right away (arm 2, HPV+treat).

The study will recruit women aged 25-54 years. Recruitment will be done mainly in HIV care clinics in South Africa. After informed consent, women will be administered short questionnaires on demographics and sexual history, and socio-economic characteristics. A health economics questionnaire focused on participant travel time and expenditures will also be administered. Women will then be asked to self-collect a vaginal sample and afterwards, a nurse will collect a cervical sample, both samples will be used for HPV testing. Any woman who refuses consent or opts out after consent will be referred to routine cervical cancer screening.

Participants will be given an appointment to the CESTA study clinics to collect their HPV result. HPV positive women will be randomised to arms 1 or 2 using the envelop method with preprinted assignment cards.

ARM 1:

A nurse will carry out a speculum examination and collect an endocervical swab to measure HIV shedding. She will then perform VIA and in half of the CESTA study clinics, the nurse will take 2-3 pictures of the cervix using the SEVIA smartphone application. 2-4 biopsies will be collected at the squamo-columnar junction (SCJ) from all quadrants that show aceto-white changes or at 12 and 6 'o clock if no acetowhite changes are visible. All eligible women for ablative treatment will be further randomised to sub-arms A (cryotherapy) and B (thermal ablation).

VIA positive women not eligible for ablative treatment will be referred to the colposcopy clinic for appropriate referral and management.

The VIA examination is inadequate if the SCJ is not entirely visible. In this case, an endocervical brush will be collected for cytological examination and the woman will be referred to colposcopy once the cytology result is known.

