3.2.2. CESTA Module 1 among HIV negative women in Senegal (see figure 3)

The study among HIV-negative women in Senegal is similar to the study design described above for HIV positive women, with the exception that, given the lower prevalence of HPV infection and disease, 7500 women aged 30 -54 will be included and randomized in a 3:1 ratio

to arm 1 (HPV + VIA + treat) and arm 2 (HPV + treat) and that treatment will be done by thermal ablation only.

Women will be recruited from the communities around the CESTA study clinics and will be invited to attend cervical cancer screening at the study clinics. Community health education organisations will be involved to create cervical cancer awareness in the community. Study information leaflets will be developed and distributed in the communities by community health workers. Where possible, invitations to participate in the study will be handed out.

After informed consent, women will be administered short questionnaires on demographics and sexual history, and socio-economic characteristics. A health economics questionnaire focused on participant travel time and expenditures will also be administered. Women will then be asked to self-collect a vaginal sample and afterwards, a nurse will collect a cervical sample, both samples will be used for HPV testing. Any woman who refuses consent or opts out after consent will be referred to routine cervical cancer screening.

Participants will be given an appointment to the CESTA study clinics to collect their HPV result. HPV positive women will be randomized to arms 1 or 2 using the envelop method with preprinted assignment cards.

ARM 1:

A nurse will carry out a speculum examination and perform VIA and in half of the CESTA study clinics, the nurse will take 2-3 pictures of the cervix using the SEVIA App. 2-4 biopsies will be collected at the SCJ from all quadrants that show aceto-white changes or at 12 and 6 'o clock if no acetowhite changes are visible. All eligible women for ablative treatment will be treated by thermal ablation.

VIA positive women not eligible for ablative treatment will be referred to the colposcopy clinic for appropriate referral and management.

The VIA examination is inadequate if the SCJ is not entirely visible. In this case, an endocervical brush will be collected for cytological examination and the woman will be referred to colposcopy once the cytology result is known.

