3.5.1. Sample size and power calculations

For the first objective, to compare the performance of the algorithms, the sample size has been calculated for the three indicators defined above. We used the percentage of HPV positive women with HSIL+ who were treated for the sample size calculation as it is the indicator that requires the largest sample size.

For HIV positive women, we assumed several features as follows: HPV testing sensitivity of 95%, 85% eligibility for ablative treatment and an overall attrition of 20% for both arms. Additionally, for Arm 1 (HPV+VIA), we assumed a VIA sensitivity among HPV positive women of 75% and 4% VIA result of suspected cancer or VIA inadequate. Using a randomisation ratio of 4:1 to Arm 1 and Arm 2, we will need to detect 125 histological HSIL+ cases in Arm 1 and 25 histological HSIL+ cases in Arm 2.

With 3000 HIV positive women attending screening, assuming 50% HPV positivity [24-26] and 50% VIA positivity, and a prevalence of 5% HSIL we will have at least 85% power to detect a difference of 24% (72.8% in Arm 1 vs 97% in Arm 2) with two-sided type error I 0.05 (see Table 2 and Table 3). In summary, under all assumptions stated, 1500 HPV positive women will need to be included.

Outcomes	Total	Arm VIA (1)	Arm HPV (2)	Difference
Total HSIL+ cases (n)	150	120	30	
Total HSIL+ HPV positive cases (n)	143	114	29	
Total HSIL+ treated (n)	111	83	28	
Total <hsil treated
(overtreatment) (n)</hsil>	742	487	254	
% of treatment among HSIL+ HPV positive women		72.8%	97.0%	24%
% of overtreatment among HPV positive women		41%	85%	44%

Table 2. Differences expected according to number of histological HSIL+ cases treated and<HSIL women overtreated in HIV positive women	Table 3. Number of HIV positive women to be screened

Sample size	Parameter	n arm VIA (1)	n arm HPV (2)
Prevalence of HSIL+	0.05		
Expected number of HIV positive women (n)	3000	2400	600
Power	>85%		

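### Section 4.2 names the big stick design for every randomisation; in its standard form it yields about 1:1, which conflicts with the 4:1 and 3:1 ratios of Module 1

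*Protocol*

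**What the plan says.** Section 4.2 is the only place where the protocol describes how allocations are generated. "Each randomisation will have its own set of cards with allocations to one of the screen-and-treat study arms", or to one of the two ablative treatments. One algorithm is then named: the "big stick design (BSD) [29] algorithm will be used". The section closes with "The same procedure will be applied on HIV positive and HIV negative women included in the study". It gives no target ratio, no imbalance limit and no version of the algorithm for unequal allocation. It also claims that the algorithm came out best for randomness among 14 methods compared.

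The ratios are fixed elsewhere:

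- South Africa: section 3.2.1 says "HPV-positive women will be randomized in a 4:1 ratio", and section 3.5.1 bases the sample size on it ("Using a randomisation ratio of 4:1 to Arm 1 and Arm 2").
- Senegal: section 3.2.2 says "7500 women aged 30 -54 will be included and randomized in a 3:1 ratio", and section 3.5.1 repeats 3:1.
- Module 2: section 3.8 sets cryotherapy versus thermal ablation at 1:1.
- Module 1 treatment cards: no ratio is given for cryotherapy versus thermal ablation.

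The Executive Summary repeats 4:1 and 3:1.

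**The concern.** The big stick design is a standard named method. Each allocation is a fair coin toss until the difference between the arm counts reaches a limit b; the next woman is then forced into the smaller arm. A bounded absolute difference means a ratio of about 1:1 in a list of any length. The rule therefore suits the 1:1 lists and conflicts with the Arm 1 versus Arm 2 lists.

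This is more than a detail left open. Section 4.2 positively states a method, applies it to the screening-arm cards in both countries, and that method as commonly defined contradicts the stated ratios. A programmer who follows the section produces the wrong list. One who adapts the method uses a procedure that the protocol does not describe, and the cited randomness property is then claimed for a different design.

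At stake are the arm sizes, the number of women allocated to treatment without triage, the number who receive VIA triage, and every arm-specific count in Tables 2 to 5.

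**Working it through.** **Inputs from the protocol.** 1500 HPV positive women randomised at 4:1 (South Africa) and 1125 at 3:1 (Senegal), from section 3.5.1. Treated proportions among HSIL+ cases of 72.8% and 97%, two-sided 0.05. HSIL+ HPV positive cases of 114/29 (Table 2) and 107/36 (Table 4). Overtreated women 487/254, total 742 (Table 2), and 323/230, total 553 (Table 4). **Assumed:** the limit b, which the protocol does not give, at 3, 5, 10 and 20.

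**1. The plan's own power.** With d = 0.242, s0 the pooled and s1 the unpooled standard error, power = Φ((d − 1.96·s0)/s1).

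- South Africa, 114/29: s0 = 0.0866, s1 = 0.0523, z = 1.38, power 91.7%. At the 125/25 given in the text: 87.7%.
- Senegal, 107/36: s0 = 0.0786, s1 = 0.0516, z = 1.70, power 95.6%.

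All agree with the stated minimum of 85%.

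**2. Planned split.** South Africa: 1500 × 0.8 = 1200 and 300, a difference of 900. Senegal: 1125 × 0.75 = 843.75 and 281.25, a difference of 562.5.

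**3. What the standard design allows.** If |N1 − N2| ≤ b, then Arm 1's share is at most 0.5 + b/(2n). For b = 20:

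- n = 1500: 0.5 + 20/3000 = 0.507
- n = 1125: 0.5 + 20/2250 = 0.509

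A simulation with b from 3 to 20 (300 lists each) gave Arm 1 between 740 and 760 of 1500, and between 553 and 572 of 1125. A limit too wide ever to bind does not help, because the coin is fair. Biasing the coin to 0.8 while still capping |N1 − N2| does not help either: one such list with b = 20 gave 758/742.

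**4. Overtreatment at 1:1.** The tables' rates are 487/1200 = 41% and 254/300 = 85%; 323/843.75 = 38% and 230/281.25 = 82%. These match the percentages printed in Tables 2 and 4. Then:

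- South Africa: 750 × 487/1200 + 750 × 254/300 = 304.4 + 635.0 = 939, against 742 planned (487 + 254 = 741 before the table's rounding).
- Senegal: 562.5 × 323/843.75 + 562.5 × 230/281.25 = 215.3 + 460.0 = 675, against 553 planned.

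**5. Power at 1:1.** The 143 cases in either country would split about 72/71: s0 = 0.0600, s1 = 0.0562, z = 2.21, power 98.7%.

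**6. A ratio-weighted form.** Capping |N1 − k·N2| with a coin of k/(k+1) gave 1199 to 1201 of 1500 for k = 4 (cap 8) and 842 to 845 of 1125 for k = 3 (cap 6), in five lists each. The planned ratios are therefore reachable with a modified rule.

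**The case against.** The strongest reply is that this is an unstated adaptation, not an infeasible method. Step 6 shows that a ratio-weighted big stick works. Section 4.2 never says 1:1, and it specifies neither the coin nor the cap. The 4:1 and 3:1 ratios are stated consistently, and each card set is prepared separately before enrolment, so a 750/750 list would be noticed on a simple count.

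Much of this stands. A reader might infer that no big stick scheme can give 4:1 or 3:1; that is true only of the unmodified design. A reader might also infer that the primary comparison would lose power or be biased. The documents do not support either: 1:1 would raise power (98.7% against 91.7% in South Africa), and a 1:1 random list is still a valid randomisation. Nor does anything show that the lists were in fact produced at 1:1.

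What does not stand is that no correction is needed. The section names a standard method without qualification, applies it to lists whose ratios that method does not produce, and cites a randomness property for it. Relying on someone to spot the mismatch leaves the method actually used undocumented.

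The alternatives also have a cost. Small permuted blocks at unequal ratios are predictable. In a 4:1 block of five, anyone who knows the boundaries can foresee (4 + 3 + 2 + 1 + 0)/5 + 1/5 = 2.2 of 5 allocations, or 44%; with sizes 5, 10 and 15 mixed and known, about 28%. Allocation here is by envelope in clinics where staff see the arm, so this matters. A ratio-weighted cap that is too tight has a similar weakness, because many allocations are then forced.

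**Conclusion.** Section 4.2 contradicts sections 3.2.1, 3.2.2 and 3.5.1, and this should be corrected before the cards are generated. Taken in its standard form, the named algorithm would move 450 women in South Africa (1200 − 750) and about 281 in Senegal (843.75 − 562.5) from Arm 1 to Arm 2. It would add about 197 expected overtreatments in South Africa (939 − 742) and about 122 in Senegal (675 − 553). The arm-specific counts in Tables 2 to 5 would no longer describe the trial. Primary power is not harmed.

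The conclusion assumes the usual definition of the big stick design (fair coin, cap on the absolute difference), which section 4.2 does not spell out. It holds for any value of b, since a wide limit leaves a fair coin. The overtreatment figures also assume that the rates in Tables 2 and 4 apply whatever the ratio, and they describe what would follow from running the rule unmodified. They are not a forecast.

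**What to change.** Revise section 4.2 as follows.

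1. State the target ratio for each card set: 4:1, 3:1, the 1:1 of Module 2, and the Module 1 cryotherapy versus thermal ablation cards, whose ratio is currently missing.
2. For Arm 1 versus Arm 2, replace the standard big stick with an unequal-allocation method. One option is a ratio-weighted big stick: coin 0.8 with a cap on |N1 − 4·N2| in South Africa, coin 0.75 with a cap on |N1 − 3·N2| in Senegal, and a cap wide enough to limit predictability. Another is permuted blocks of randomly mixed sizes.
3. Keep the cap or the block sizes in a document that clinic staff do not see.
4. Limit the sentence on comparative randomness to the 1:1 lists that use the standard design.
5. Count the cards per arm in each list before release.

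The cost is one paragraph and a changed R routine before printing. No extra women are needed, and the sample size section can keep its stated ratios.

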4.3. Duration of subject participation

For all women, the study will include one round of HPV testing. HPV negative women will finish their participation in the study after this first round.

In Module 1, all HPV positive women with or without VIA triage will have a follow-up HPV test at 12 months, and will end their participation if the HPV test at 12 months is negative or after <CIN2 histology on biopsy collected at the colposcopy visit or after treatment (LLETZ or other) for CIN2+.

In Module 2, women with CIN2/3 on biopsy will be randomized into TA or cryotherapy. Women that are ineligible for ablative treatment will be referred to colposcopy for appropriate management and all other women with LSIL+ cytology will be exited from the study and referred back to the ARV clinic for follow up according to South African standard of care. All treated women will attend a FU visit at 12 mo. and 24 mo. with HPV testing, VIA, and colposcopy-directed biopsies on HPV positive women to detect remaining/recurrent disease. At the time of exit, all women will be given clear indications on how to continue with regular screening or with any needed follow-up under the local health system.

5. Ethical considerations

The study will be approved by the IARC and local ethical committees of participating countries: currently being the Biomedical Research Ethics committee (BREC) at the University of KwaZulu-Natal and the "Comité National d'Ethique pour la Recherche en Santé" under the Ministère de la Santé et de l'Action Sociale, Dakar. All women in the study will sign informed consent forms approved by IARC's and the local ethical committees.

The informed consent form will include details on the background, procedures of the study, risks and benefits, statement of confidentiality, specimen use and study staff to contact (informed consent document in annex).

The study is considered minimal risk and the procedures are standard practice in cervical cancer screening programs. The clinical procedures to be performed were developed by a team of clinicians including colposcopists mainly considering the safety of the participants in terms of reduction of cervical cancer risk, and all the procedures are consistent with standard medical practice and/or WHO recommendations, including thermal ablation.

